For RCT phase, structured clinical interviews will take place at Baseline (week 0) and posttest (within 4 weeks of final session). Self reports/surveys will take place at Baseline (during week 0) and at posttreatment (during final session). For drop out Veteran participants, posttest surveys will be completed 16 weeks post-session 1 and the posttreatment clinical assessment will be done within 4 weeks of that posttest survey. For late treatment completers (i.e., treatment takes more than 16 weeks), all posttest surveys and post clinical interviews will be delayed but will be done no later than 24 weeks post-session 1.

For the IC phase, weekly surveys will be given for the first 2 weeks of treatment (session 2a, and 2b). For the RCT phase, weekly surveys will be given during weeks 2, 4, 5, 6, 8, 10 and 12 of treatment. For participants, the weekly surveys during week 2 and 8 will be lengthier and more thorough. All structured interviews (CAPS-5³ and SCID-5-CT)¹² will be administered by trained and supervised assessors who are blinded to condition. Assessors will be trained and supervised weekly by [name], a licensed clinical psychologist with expertise in conducting structured diagnostic clinical interviews and assessing and intervening with patients experiencing mental health crises. For mailed assessments, we will use CCDOR's well-established modified-Dillman protocol with repeated mailings and an incentive (incentive schedule described below).⁶ For surveys of Veterans with PTSD, our team's response rates

have ranged from 55% to 85%. Given the short interval between assessments, we will include a telephone call reminder and an offer telephone administration to optimize response rates.⁶

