Power analyses are based upon our ability to detect a clinically meaningful difference between our two treatment conditions on PTSD symptom severity using the PCL.⁵ A five-point difference on the PCL is the minimal threshold for determining if an individual has responded to treatment (i.e., differences not due to chance); a ten point difference is the minimal threshold for clinically relevant differences.⁷ Smaller differences are unlikely be clinically meaningful. Analyses take into account our repeated measures, two-armed design and estimates of variance and auto-correlations between repeated PCL assessments from our prior work (Project HomeFront, Time 1 PCL SD = 12.16; Time 2 PCL SD = 14.8; Time 1 and Time 2 PCL, $r = .61$). Using a plausible range of auto-correlations ($r = .50\text{-.70}$) and standard deviation estimates (SD = 12.16-14.8), and assuming 20% missingness on posttreatment PCL scores ($n = 124$), we are sufficiently powered (80%) to detect a 4.1 to 5.8 point difference between treatment conditions on posttreatment PCL total scores ($d = .34\text{-.40}$). Analyses will rely on the latest version of the PCL (i.e., the PCL-5²). Data currently is unavailable translating clinically meaningful differences on the PCL to the PCL-5; however, preliminary work suggests the ranges described above will be similar for the PCL-5.²

5.6B. Data Analysis.

5.6B1. General Approach. The study is a two arm patient-level randomized superiority trial, nested within 3 sites, each with 4 providers. Analyses will consider this design structure and follow intent-to-treat methodology. First, we will examine the distribution of all study variables (data verification). Second, we will evaluate bivariate associations between condition assignment and study outcomes and covariates to determine unadjusted measures of effect and identify imbalance in baseline covariates. Due to randomization, we do not anticipate imbalances in baseline characteristics between groups, but we will adjust for any differences by including these variables as covariates. Third, we will examine the impact of missing survey items and adjust for their influence. After testing and identifying the mechanism underlying any missingness (MAR,NI), we will use the implied specific imputation methods to impute missing covariates and factors and generate five imputed data sets. Final analyses will include complete case analysis and an aggregated analysis based on the multiply imputed data.

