5.6B2. Aims 1 and 2. After completing the above steps, we will test our hypothesis for Aim 1 using generalized linear mixed models. The number of sessions attended, within the assumed and appropriate fitted distribution, will be modeled with treatment and site as fixed effects and a random provider effect (clustering by provider). Analyses for Aim 2 will similarly use mixed models to examine differences between conditions on PCL-5 scores over time, modeling the treatment, time, and treatment by time effects. Secondary analyses will examine CAPS-5 scores and loss of diagnosis on the CAPS-5 (both PTSD diagnosis and subclinical PTSD diagnosis) to facilitate comparisons with existing and ongoing research on treatments for PTSD. We will also examine differences between conditions on PHQ-9, WHO-QOL, QRI, and CSQ-8 scores.

Analyses will follow the same general approach as Aim 1, with some exceptions. First, some indices are dichotomous (i.e., presence or absence of PTSD or subclinical PTSD diagnosis). Models will be fit using appropriate distribution and link functions (i.e. for binomial distribution and logit links for PTSD diagnosis; whereas mean group differences might fit a normal distribution). Second, unlike Aim 1, which relies on administrative data, Aim 2 outcomes rely on

self-report data, where some attrition is inevitable. Analyses will include examining group differences using available data, as well as analyses employing imputation as described above. To study the time-dependence of clinical outcomes, we will model the first-order transition probabilities of Markov chains (under treatment and control) with auto regressive random intercepts, random slope (provider), and fixed effects for treatment, site, sessions attended, and homework compliance. Lastly, we will explore indirect pathways from family supported PE to improved treatment outcomes through greater adherence (e.g., treatment condition → session attendance → PTSD symptoms), using approaches for testing indirect effects described below.

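### Section 5.6B2 neither prespecifies baseline adjustment for the Aim 2 outcomes nor names the posttreatment PCL-5 contrast as the test; adjusting for baseline would add modest precision at almost no cost.

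*Combined protocol and SAP*

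**What the plan says.** Section 5.5A.4 makes PCL-5 the main outcome for Aim 2. Section 5.6B2 analyses it with "mixed models to examine differences between conditions on PCL-5 scores over time, modeling the treatment, time, and treatment by time effects". No baseline covariate, equal-baseline constraint, list of occasions, coding of time or test contrast is given.

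For Aim 2 outcomes more widely, 5.6B2 adds: "Analyses will follow the same general approach as Aim 1, with some exceptions". The Aim 1 model in the same section has treatment and site as fixed effects and provider as a random effect.

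Section 5.6B1 expects no baseline imbalance because of randomisation, "but we will adjust for any differences by including these variables as covariates". Adjustment therefore depends on what is observed.

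The Aim 2 power statement in 5.6A2 concerns posttreatment scores: "we are sufficiently powered (80%) to detect a 4.1 to 5.8 point difference between treatment conditions on posttreatment PCL total scores". Its inputs are "Time 1 PCL SD = 12.16; Time 2 PCL SD = 14.8", a pre-post correlation of .61, correlations of .50 to .70, and 124 analysed Veterans.

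On occasions, sections 3.0 and 5.5A describe Aim 2 as a comparison from baseline to posttreatment. Section 5.5A.4 also lists PCL-5 during treatment, and under 5.5A.2 "weekly surveys will be given during weeks 2, 4, 5, 6, 8, 10 and 12 of treatment".

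**The concern.** Baseline is measured before treatment and, under randomisation, any arm difference there is chance. A model with a free treatment main effect lets the arms differ at baseline and subtracts that chance difference in full. A baseline-adjusted model subtracts only the part that predicts the posttreatment score, so its standard error is never larger in expectation. The rule in 5.6B1 is no substitute: it sets no threshold, depends on the data, and does nothing for a strongly prognostic baseline that happens to be balanced.

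The second issue is what is tested. If seven in-treatment scores join baseline and posttreatment, treatment by time could be a joint test over all follow-up occasions, a linear slope, or a single contrast at posttreatment. These are different tests, and the choice could be made after the data are seen.

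**Working it through.** **Inputs.** From 5.6A2: s1 = 12.16, s2 = 14.8, r = .61 (range .50-.70), n = 124, so 62 per arm. The section states neither alpha nor sidedness; 0.05 two-sided is assumed. Provider clustering is ignored.

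**The plan's own figure.** Detectable difference = SD × f(r) × (1.960 + 0.842) × √(2/62) = SD × f(r) × 0.5032. Over SD 12.16-14.8 and r .70-.50:

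| Analysis | f(r) | Range (points) |
|---|---|---|
| Baseline-adjusted | √(1 − r²) | 4.37-6.45 |
| Difference in change | √(2(1 − r)) | 4.74-7.45 |
| Posttreatment only | 1 | 6.12-7.45 |

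None reproduces 4.1 to 5.8. That is a separate matter, but it means that the stated range cannot tell us which analysis was intended.

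**Precision with the two stated SDs.** Per-person variances (points²) at r = .61:

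- Baseline-adjusted: s2²(1 − r²) = 219.04 × 0.6279 = 137.5.
- Difference in change: s1² + s2² − 2·r·s1·s2 = 147.87 + 219.04 − 219.56 = 147.3.
- Ratio: 137.5 / 147.3 = 0.933, a reduction of 6.7%.

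At r = .50 the ratio is 164.3 / 186.9 = 0.879; at r = .70 it is 111.7 / 115.0 = 0.972. The reduction is thus 3-12% over the plan's range. With equal SDs the ratio is (1 + r)/2, or 0.75, 0.805 and 0.85 at r = .50, .61 and .70: a reduction of 15-25%.

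**What that means at r = .61, 62 per arm:**

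| Analysis | Detectable at 80% power | Power for 5.8 points |
|---|---|---|
| Baseline-adjusted | √137.5 × 0.5032 = 5.90 | 78.6% |
| Difference in change | √147.3 × 0.5032 = 6.11 | 75.8% |
| Posttreatment only | 14.8 × 0.5032 = 7.45 | 58.8% |

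In sample-size terms, 62 / 0.933 = 66.4, so the gain is worth about four analysed Veterans per arm.

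These figures treat the data as 62 complete pairs per arm. A mixed model that also uses the baselines of the other 16 per arm narrows the gap. With b = r·s2/s1 = 0.742, the per-arm variance of change is 137.5/62 + (1 − b)² × 147.87/78 = 2.218 + 0.126 = 2.344, against 2.218 adjusted: a reduction of 5.4%.

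**Other scales.** If CAPS-5, PHQ-9, WHOQOL and QRI are analysed at posttreatment with no baseline term, adjustment removes a fraction r² of the variance. The documents give no r for these scales.

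**Which test.** Illustration only: nine occasions (weeks 0, 2, 4, 5, 6, 8, 10, 12, 16), SD 14.8 throughout, baseline-to-posttreatment r = .61, 62 per arm, 5.8 points at posttreatment. Where two figures are given, the first is for compound symmetry and the second for autoregressive correlation.

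- Effect building linearly: 8-df joint test 57% or 36%; linear slope 88% or 70%; pre-post change 70%; baseline-adjusted posttreatment contrast 79%.
- Effect only at posttreatment: joint test 63% or 93%. Under compound symmetry the fitted slope implies 4.1 points at week 16, not the true 5.8.

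No test wins everywhere, but they differ enough that the choice should be fixed in advance.

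**The case against.** The planned mixed model is unbiased under randomisation and does use baseline, as the first repeated measure. With only two occasions, as sections 3.0 and 5.5A suggest, treatment by time is one contrast whose expected value equals the posttreatment difference. All of this stands: on that reading the target is right and only precision is lost, and on the plan's own SDs the loss is small.

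A reader might go further in four ways that the documents do not support.

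- That the plan tests treatment by time across every occasion. Section 5.6B2 does not say which occasions enter; the text is open, not committed to that.
- That including the in-treatment scores must cost power. The illustration shows that it can go either way.
- That the clinical scales certainly lack a baseline term and lose a quarter to a half of their precision. The reference to the Aim 1 approach may mean only the model family, and such a figure would need PCL correlations borrowed for other scales.
- That the trial's sample size rests on this contrast. Section 5.6A makes session attendance the primary outcome; the PCL calculation supports Aim 2.

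One practical objection also stands. Section 5.4C requires baseline to be retaken if therapy would start two months after it was collected, and the documents do not say that retakes precede randomisation. A fix must therefore say which baseline is used.

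**Conclusion.** The point holds as a nearly free improvement, not as an error that invalidates Aim 2. As written, the PCL-5 contrast from baseline to posttreatment is valid but less precise than it need be: about 7% of variance at r = .61, or 3-12% over the plan's correlation range. It would be 15-25% if the SDs were equal, which the plan's own data do not show. These sizes rest on two-sided 0.05, 62 complete pairs per arm and no provider clustering.

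Separately, the plan does not settle whether in-treatment scores enter the model or name the posttreatment contrast as the test. For the other clinical scales the wording permits an analysis with no baseline term, and the loss there could be larger by an amount that the documents do not allow us to calculate.

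**What to change.** State in 5.6B2 that:

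1. PCL-5 is analysed with time as categorical and the baseline mean constrained equal across arms. The alternative is baseline as a covariate, with baseline then removed from the outcome vector.
2. The occasions in the model are listed, and the single Aim 2 test is the treatment contrast at posttreatment, whether or not in-treatment scores are included.
3. CAPS-5, PHQ-9, WHOQOL and QRI are analysed with their own baseline value as a covariate, whatever imbalance is seen.
4. Baseline means the last value collected before randomisation; a retake after randomisation is not used as the adjustment baseline.

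The cost is a few sentences of analysis text. No new data are needed: section 5.3 requires the baseline survey before randomisation, and section 5.4B makes the baseline CAPS-5 part of final eligibility. The only operational step is to date each baseline against randomisation, so that retakes can be classified.

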Aim 1: To improve Veterans' adherence to PE through engaging families in care._

Aim 2: To improve the clinical outcomes of Veterans receiving PE through engaging families in care._

Aim 3: To examine barriers/facilitators of implementing family support for PE.

Exploratory Aim: To identify mechanisms underlying adherence differences between treatment conditions._

Methods. We are proposing a practical randomized controlled trial to compare Veteran adherence, and to PE with and without family attendance at PE's educational sessions, with the ultimate goal to improve Veterans' clinical outcomes. For Aim 3, we will use a concurrent process evaluation to identify potential implementation facilitators and barriers to family involvement in PE within VA. Participants will include Veterans with clinically significant symptoms of PTSD within VA across three sites, plus a family member or friend of the Veteran. Aim 1 outcome variables include session attendance and homework compliance. Aim 2 outcomes include PTSD symptom severity, depression, quality of life, and relationship functioning, measured over the course of treatment. Key social influences (Exploratory Aim) will be assessed through brief weekly self-reports.

List of Abbreviations

BSI	Brief Symptom Inventory
BFT	Behavioral Family Therapy
CAPS-5	Clinician-Administered PTSD Scale for DSM-5
CCDOR	Center for Chronic Disease Outcomes Research
CDA	Health Services Research and Development Career Development Award
CEQ-PTSD	Credibility/Expectancy Questionnaire, adapted for EBPs for PTSD
Co-I	Co-Investigator
Co-PI	Co-Principal Investigator
CPRS	Computerized Patient Record System
CPT	Cognitive Processing Therapy
CSQ-9	Client Evaluation of Services Questionnaire
CTS-2	Conflicts Tactics Scale-2
SF CTS-2	Short Form of the Conflicts Tactics Scale-2
EBP	Evidence Based Psychotherapy
FES	Family Environment Scale
HSR&D	Health Services Research and Development
IC	Intensive Coaching
IIR	Investigator-Initiated Research
IRB	Institutional Review Board
MI	Motivational Interviewing
OCD	Obsessive Compulsive Disorder
OEF	Operation Enduring Freedom
OIF	Operation Iraqi Freedom
OMHS	Office of Mental Health Services
PCL	Posttraumatic Stress Disorder Checklist (DSM-IV)
PCL-5	Posttraumatic Stress Disorder Checklist (DSM-5)
PE	Prolonged Exposure
PHQ-9	Patient Health Questionnaire
PI	Principal Investigator
PTSD	Posttraumatic Stress Disorder
QRI	Quality of Relationships Inventory
RCT	Randomized Controlled Trial

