2.0 Introduction

Post-traumatic stress disorder (PTSD) occurs in as many as 1 in 5 combat Veterans¹⁵⁻¹⁷ and is associated with a host of negative, long-term consequences, including high rates of suicide and traumatic death.^{47,48} Trauma-focused cognitive-behavioral therapies for PTSD, like Prolonged Exposure Therapy (PE), result in significant improvement for many patients.²² While these proven psychotherapies have been disseminated in VA, poor adherence interferes with treatment response.^{49,50} Previous reviews of treatment completion in randomized controlled trials find that one in five patients dropout from active, change-focused treatments for PTSD, including PE and Cognitive Processing Therapy (CPT).²⁶ Rates of PE/CPT drop out are even higher

among Veterans,^{27-29;50;51} with estimates across studies converging around 35%.²⁷⁻²⁹ Importantly, those with the greatest need for PTSD treatment are likely at the highest risk for premature termination.²³ Similar problems with tolerating treatment are found among cognitive behavioral therapies, broadly.²⁶ Consequently, adherence, in and of itself, was identified as a top priority for real-world use of Evidence-Based Practices (EBPs) by the World Health Organization, Institute of Medicine, and the US Surgeon General.^{22;32-34}

PE addresses PTSD through confronting trauma memories to reduce fear, facilitate emotional processing, and promote new learning.⁵² Disrupting entrenched patterns of avoiding trauma reminders requires persistence by Veterans, through daily trauma exposure exercises at home. While these exercises require considerable Veteran commitment, they are similar to those of other demonstrated, effective, cognitive-behavioral therapies,⁵³ and psychotherapies with homework are associated with better treatment outcomes.^{25;54} Meta-analysis indicates 24% more patients will improve just from adding homework to a given psychotherapy.⁵⁴ Across multiple meta-analyses, compliance with these assignments predicts treatment response.^{24;25;53;56;57} Additionally, adherence to more challenging homework assignments, like exposure

[figure not shown]

Figure 1. Conceptual Model Underlying Partner Supported PE

exercises, predicts treatment response better than adherence to less difficult exercises (i.e., readings, self-monitoring).⁵⁵ Ultimately, the key for optimizing Veterans' gains from PE likely lies with efforts to maximize Veterans' engagement, through

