The Theory of Planned Behavior has been criticized for a focus on 'rational' decision making at the expense of non-rational processes, such as implicit cognitions (cognitive short cuts, like 'anxiety is bad'), immediate influences (including social network members), and emotional reactions.^{74;75} Patients make day-to-day decisions about adherence that are influenced by non-rational processes.⁷⁴ PE providers have 1-2 formal sessions per week with Veterans; they are limited in their ability to address non-rational processes between sessions. Through altering social influences, we may mitigate negative influences of non-rational processes on decision making through helping SPs provide appropriate support when Veterans discuss feelings about the treatment or its tasks, increasing the frequency at which SPs encourage Veterans to persist in PE, and contributing to an environment that broadly supports change in Veterans' day-to-day lives. Ultimately, through optimal Veteran engagement in PE, we hope to maximize the gains that Veterans can achieve in treatment.

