3.0 Objectives

The objective of the proposed study is to evaluate the effectiveness of family support as a tool to improve Veterans' EBP adherence. We are proposing a randomized practical clinical trial employing an effectiveness-implementation Hybrid 1 design.⁴² This design will focus on external validity, flexibility, and liberal inclusiveness of the patient population.^{1;4;43;44} We will also identify potential facilitators and barriers of involving family in PE within VA. Our central hypothesis is that when families support Veterans' PE participation through attending PE's educational sessions (family supported PE), adherence will improve over PE as delivered in routine care.

Aim 1: To improve Veterans' adherence to PE through engaging families in care.

We hypothesize that when families support Veterans' PE participation through attending PE's initial educational sessions, Veterans' attendance to PE (H1a) and homework compliance (H1b) will improve, compared to PE as typically delivered.

Aim 2: To improve the clinical outcomes of Veterans receiving PE in routine care through engaging families in Veterans' treatment.

We hypothesize that family supported PE will be more effective than standard PE in reducing PTSD severity and comorbid problems (depression, quality of life, relationship functioning) from pre-to-posttreatment.

Aim 3: To examine barriers/facilitators of implementing family supported PE through a mixed-method, multi-stakeholder process evaluation¹⁰⁰ with patients, providers, and mental health leadership.

Exploratory Aim: To identify mechanisms underlying differences in adherence between treatment conditions.

We will explore if differences in adherence between family supported PE and standard PE are mediated by changes in key social influence variables, including family perceptions of treatment credibility, family support for Veterans' PE participation, and families' accommodation for PTSD symptoms.

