5.6 Data Analysis

Figure 3. CONSORT Diagram

5.6A. Power analysis and sample size for the RCT phase.

Based on annual rates of patients initiating EBPs for PTSD at each site, we estimate 1751 Veterans will be referred for EBPs over the recruitment period (27 months). Based on response rates for Project HomeFront, we anticipate 50% (n = 876) will be interested in research. See Figure 3 for recruitment flow. Estimates are conservative and incorporate Project HomeFront data, including that 8% will not have eligible SPs, 34% of Veterans will be unwilling to ask SPs to participate, and 20% of SPs will not be interested. To support recruitment success, we will also use study fliers and brochures strategically placed in appropriate clinic locations. We will contact patients until we reach 156 patients randomized (78 in each arm).

We expect to enroll 2 subjects per month, per site, during recruitment for a total n of 156 Veterans and 156 SPs.

Session attendance serves as the primary outcome. Analyses below indicate our proposed minimum n of 156 is sufficient to detect clinically meaningful differences between standard PE and family supported PE on Aim 1 and Aim 2 outcomes. Data analysis will take place at the Minneapolis VA Health Care System. Individuals involved in data analysis (quantitative and qualitative) will include [name] and Drs. [name], [name], [name], [name], and [name].

5.6A1. Aim 1. Preliminary Project HomeFront data indicate the average number of sessions attended is 7.30 ($SD = 4.45$). Seventy-eight participants in each arm yields 80% power to detect a two session difference between treatment conditions. A two session improvement corresponds to an effect size of ($d = 0.43$), slightly below conventions for a moderate effect size ($d = .50$). A greater sample size could detect smaller effects, but these are unlikely to be clinically meaningful. An alternative approach is to power the study based on a minimally

clinically significant increase in rates of treatment completion (e.g., at least 10%). However, given the increased power needed to detect change in a dichotomous outcome, this would not be feasible; we would need at least 692 subjects for 80% power.

5.6A2. Aim 2 (family supported PE will lead to greater reductions in PTSD symptoms than standard PE).

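### The supplementary Markov model in 5.6B2 adjusts treatment for sessions attended and homework compliance, so its treatment term leaves out any benefit gained through adherence and is not the effect of family supported PE

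*Combined protocol and SAP*

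**What the plan says.** Section 5.6B2 introduces the model as follows: "To study the time-dependence of clinical outcomes, we will model the first-order transition probabilities of Markov chains (under treatment and control". Its terms are "auto regressive random intercepts, random slope (provider), and fixed effects for treatment, site, sessions attended, and homework compliance". Treatment and both adherence measures therefore sit in one model.

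Elsewhere the plan treats those two measures as results of the intervention:

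- The Abstract states: "Aim 1 outcome variables include session attendance and homework compliance".
- Section 3.0 hypothesises that "attendance to PE (H1a) and homework compliance (H1b) will improve, compared to PE as typically delivered".
- Section 5.6A adds: "Session attendance serves as the primary outcome".

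The plan also places them on the path to clinical benefit. Section 2.1 says: "Ultimately, through optimal Veteran engagement in PE, we hope to maximize the gains that Veterans can achieve in treatment". Section 2.0 says of homework: "Across multiple meta-analyses, compliance with these assignments predicts treatment response". Directly after the Markov model, 5.6B2 announces that "we will explore indirect pathways from family supported PE to improved treatment outcomes through greater adherence", and gives attendance as the example of the intermediate step.

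The main Aim 2 analysis is a different model in the same section. It is a mixed model of PCL-5 with arm, time and their interaction, and no adherence terms are named.

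**The concern.** A treatment coefficient adjusted for a consequence of treatment no longer measures the total effect. Two things happen here.

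First, the part of the benefit that runs through attendance and homework is credited to those covariates and leaves the treatment term. Family support is meant to work largely by that route, so the loss may be substantial.

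Second, comparing arms at equal attendance breaks the balance that randomisation created. If family support raises attendance, a supported Veteran with a given count would on average have attended less without support. Any unmeasured trait that affects both attendance and symptoms then differs between the compared groups.

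Timing is a further gap. The plan does not say how sessions attended is coded in this model. If it were the final count, later attendance would help explain earlier transitions, for example from week 2 to week 4.

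At stake is the reading of one supplementary analysis. A weak or null treatment term could be reported as conflicting with the intent-to-treat PCL-5 comparison when the two estimate different quantities.

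**Working it through.** **Inputs from 5.6A1 and 5.6A2.** Mean sessions 7.30, SD 4.45; target difference 2 sessions; 78 per arm; later PCL SD 14.8; smallest detectable PCL difference 4.1 points. The 4.1 is the lower end of a detectable range and serves here only as a scale, not as an expected effect.

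**The plan's own figure.** With two-sided alpha 0.05 (assumed; the plan states none), n per arm = 2(1.960 + 0.842)² × 4.45² / 2² = 77.7, so 78, with 80.1% power. The figure for the main mediator reproduces and is not in dispute.

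**Attenuation.** Let T be arm and S sessions. Family support adds 2 sessions and changes PCL-5 by −4.1 in total (negative means improvement). If a share m runs through S, the treatment term adjusted for S is −4.1 × (1 − m):

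- m = 0.5: −4.1 × 0.5 = −2.05
- m = 1: 0

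No common cause is needed for this loss.

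**Adding an unmeasured common cause U (assumed).** Take S = 7.3 + 2T + 2.5U + error and homework H = 0.5T + 0.5U + error, with U of variance 1, within-arm variance of S 4.45² = 19.80, and within-arm variance of H set to 1. Then cov(U,S) = 2.5, cov(U,H) = 0.5 and cov(S,H) = 2.5 × 0.5 = 1.25. The determinant is 19.80 × 1 − 1.25² = 18.24. Regressing U on S and H within arm gives:

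- k_S = (2.5 × 1 − 1.25 × 0.5) / 18.24 = 0.103
- k_H = (19.80 × 0.5 − 1.25 × 2.5) / 18.24 = 0.372

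At equal S and H, family-arm Veterans are lower on U by 2 × 0.103 + 0.5 × 0.372 = 0.39. If U changes PCL-5 by g points per SD, the adjusted treatment term is −4.1(1 − m) − 0.39g.

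| Effect of U on PCL-5 (g) | Half mediated | Fully mediated |
|---|---|---|
| 0 | −2.05 | 0 |
| −2 (U raises attendance, improves symptoms) | −1.3 | +0.8 |
| −4 | −0.5 | +1.6 |
| +2 (U raises attendance, worsens symptoms) | −2.8 | −0.8 |
| +4 | −3.6 | −1.6 |

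The unadjusted effect is −4.1 in every cell. With within-arm variance of H at 1.25 the multiplier is 0.36 in place of 0.39, and the pattern is the same.

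**The planned model type.** A two-state first-order Markov logistic model was simulated with 156 Veterans, 8 occasions and 600 runs per setting. Provider and autoregressive random effects were left out. Positive log-odds favour family support.

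| Benefit mediated | Common cause | Without adherence terms | With them | Runs negative with them |
|---|---|---|---|---|
| All | None | 0.40 | 0.02 | 46% |
| All | Moderate | 0.33 | −0.17 | 83% |
| All | Strong | 0.27 | −0.31 | 93% |
| Half | None | 0.46 | 0.25 | 6% |
| Half | Moderate | 0.39 | 0.06 | 37% |
| Half | Strong | 0.33 | −0.08 | 66% |

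Only common causes that raise attendance and improve symptoms were simulated here. Without the adherence terms, 0% to 9% of runs were negative.

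**Timing.** Section 5.5A.1 has providers log the dates of attended, missed and cancelled sessions. Table 3 lists homework compliance as a provider report during treatment, under the weekly column. Counts up to the start of each interval can therefore be built from data already collected.

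**The case against.** The strongest reply is that the plan never offers this model as its test of the treatment. Its stated purpose is time-dependence, the Aim 2 comparison is the PCL-5 mixed model, and the sole primary outcome is attendance. The plan also knows that adherence is a mediator, since it tests indirect pathways separately, and a model with treatment and mediators together is a normal part of such work. This stands as a limit on scope. It does not remove the point, because the Markov model is set up to compare treatment with control, the mediation work is a separate step, and nothing labels this treatment term a direct effect or states the assumptions that reading needs.

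A reader might infer that a real benefit would turn into apparent harm whenever the central hypothesis is true. The documents do not support that. The hypothesis in 3.0 is that adherence improves, not that all clinical benefit passes through it. In the linear illustration, harm appears only with full mediation plus a common cause that raises attendance and improves symptoms. Full mediation through attendance alone needs 4.1 / 2 = 2.05 points per session, a within-arm correlation of 2.05 × 4.45 / 14.8 = 0.62, which the documents do not give. The opposite sign is also plausible: 5.1C lets therapy be extended as needed, so slower responders may attend more. The transition simulation at half mediation and its strongest common cause averaged −0.08, near zero.

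A reader might also infer that sessions attended enters as an end-of-treatment total. The plan defines a count for the Aim 1 outcome but does not say how this covariate is coded. The timing problem is conditional on that choice.

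**Conclusion.** The point holds for the supplementary Markov model only. As written, its treatment term excludes benefit gained through adherence and should not be read as the effect of family supported PE on clinical course. On a 4.1-point scale the loss is about 2 points at half mediation and about 4 points at full mediation. Further bias from a common cause can go either way, and apparent harm is a special case needing near-complete mediation and a common cause of one particular sign. The mediated share, the strength of the common cause and the homework variance are assumptions shown as ranges; the direction of the attenuation rests only on adherence carrying part of the benefit, as the plan itself proposes. No conclusion from the primary attendance model or the main PCL-5 mixed model is at risk. The coding of sessions attended is unspecified and should be stated.

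**What to change.** In 5.6B2, remove sessions attended and homework compliance from the Markov model whose treatment term is interpreted. Keep treatment, site, provider and the prior state.

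If the link between adherence and later symptoms is of interest, add a second model in which sessions and homework are accumulated up to the start of each interval. State that its treatment term is a conditional association and not the treatment effect.

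The cost is a sentence or two in the analysis section. Session dates and weekly homework ratings are already collected, and neither the sample size nor any study procedure changes.
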